5.1.3 Safety Committee

The Safety Committee's membership will be composed of a minimum of the Sponsor team (Sponsor Senior Physician and Sponsor Senior Scientist or an appropriate delegate) and Principal Investigator (or an appropriate delegate). Additional members may be invited as needed (e.g. PK scientist, project manager).

All data reviewed at the dose escalation meeting (safety, tolerability and available PK data) will be subjected to a quality control review.

CONFIDENTIAL**5.1.4 Stopping Rules**

Dosing for any individual subject will be stopped if the subject experiences a possibly drug-related serious adverse event or a possibly drug-related significant non serious adverse event, which in the opinion of the study physician, Principal Investigator or Chief Investigator (Sponsor's medical representative), warrants discontinuation of the study for that subject's well being.

In Parts A and B, following consultation with the Sponsor, dose escalation will stop if:

- Clinically relevant signs or symptoms of similar nature, occur in 2 or more subjects within a group/cohort, which in the opinion of the Investigator warrant stopping of dose escalation.
- A serious adverse event (SAE) in one or more subjects thought to be related to the study drug or a severe AE in two or more subjects thought to be related to study drug. If this criterion is met the study will be halted. If, following internal review, it is deemed acceptable to restart the study a substantial amendment will be submitted to the Competent Authority.
- Moderate nausea or vomiting that prevent subjects from eating a meal on 3 or more occasions on 2 successive days are seen in 2 or more subjects in a group.
- Severe diarrhoea, defined as 7 or more episodes, rated as ≥ 5 on the Bristol Stool Chart, in 1 day for 2 consecutive days are seen in 2 or more subjects in a group.
- The mean systemic exposure is predicted to exceed a C_{max} of 440 ng/mL and/or $AUC(0-72h)$ of 28,100 ng·h/mL i.e. systemic exposure will be no greater than that the lowest exposure at the NOAEL for male rats (30 mg/kg/dose). This limit is chosen on the basis that rats are expected to be the species that will most closely predict toxicity in humans.

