5.1.1 Part A (Single Ascending Dose)

Part A is a double blinded, randomised, placebo controlled, single ascending dose study (SAD). The following reflects the plan prior to execution of Part A. Approximately 28 eligible subjects will be enrolled in 5 sequential cohorts of overweight but otherwise healthy male subjects (BMI range of 25 to 38 kg/m²). No subject will be a member of more than 1 cohort.

Cohort 1 will comprise 4 subjects (3 active and 1 placebo). In cohort 1, each subject will be dosed in three treatment periods (TPs) with three ascending dose levels (proposed doses 1 mg, 4 mg, 8 mg Y14). The subjects will be randomised to either placebo or active treatment at each of these visits, i.e. different subjects will receive placebo in each TP. There will be a minimum washout period of 1 week between Day 1 of each TP. If any subject in Cohort 1 drops out between doses, they will be replaced.

Cohort 2 onwards will comprise 6 subjects (5 active and 1 placebo) for each cohort. Each volunteer in Cohort 2 onwards will only be dosed once in one TP. Proposed doses for cohorts 2-5 are 16 mg, 32 mg, 64 mg and 96 mg. All doses, and peptide concentrations are subject to change according to safety and PK review.

Up to eight additional cohorts of up to 6 subjects each (i.e. up to 48 subjects in total) may be enrolled if recommended by the Safety Committee (see Section 7.1.4) to increase scientific value of this study, e.g. to verify PK data or further characterise PD markers.

For each dose level, subjects will be randomised to receive a single dose of Y14 or matching placebo by SC injection (with fractionation if needed). A sentinel dosing strategy will be used as outlined in Table 5.1.

Table 5.1 Dosing Schedule: Part A

Cohort	Treatment Periods	Dosing Session	Number of Subjects	
			Y14	Placebo
1	1	Sentinel subjects	1	1
		Non-sentinel subjects	2	0
1	2-3	Sentinel subjects	0	0
		Non-sentinel subjects	3	1
2 onwards	1	Sentinel subjects	0	0
		Non-sentinel subjects*	20	4

*May be increased if additional groups are dosed

In Cohort 1, TP1, the first two subjects will be randomised such that 1 subject receives Y14 and 1 subject receives placebo. This sentinel pair will be dosed first and will be observed for at least 48 h before study drug is administered to the remainder of the cohort. Safety (vital

CONFIDENTIAL

Synoptic Clinical Study Protocol
Version 2.0 - 05/08/2017

EudraCT Number: 2017-000380-33

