signs, ECGs, and clinical laboratory safety tests), and tolerability (adverse event profile) data up to and including 24 h postdose will be reviewed by Covance's clinical team prior to dosing the remaining subjects at that dose level. Dosing of the subsequent subjects in cohort 1 will be at the discretion of the Principal Investigator.

Treatments will be administered double blinded (except for Cohort 1, TP1 where it will be known that the 3rd and 4th subjects will receive the active dose); subjects will be blinded with regard to treatment and clinical staff will remain blinded with regard to treatment until the Safety Committee meeting.

An interval of at least 7 days will separate the dosing of the last subject in one cohort and dosing of the first subject in the next cohort to permit a timely review and evaluation of interim safety, tolerability and PK data. Safety, tolerability and PK data will be reviewed up to 48 hours post-dose prior to the dose escalation decision. If T_{max} is significantly later than predicted, PK data to a later timepoint may be reviewed prior to the dose escalation decision. The data of up to at least 3 subjects receiving Y14 in cohort 1 and 4 subjects, (i.e. a minimum of 3 subjects receiving Y14) in cohort 2 onwards will be reviewed before dose escalation.

Following a 28-day screening period eligible subjects will be admitted to the clinical unit on Day -1 (1 day prior to dosing) for eligibility checks and baseline assessments. On Day 1 subjects will receive a single dose of Y14 or placebo by SC injection, and will remain in the clinical unit under medical supervision until 72 h postdose (Day 4) or until C_{max} is achieved, whichever is the later.

Safety monitoring will include assessment of adverse events (AEs), physical examination, 12-lead ECGs, vital signs (blood pressure pulse rate and body temperature) and clinical laboratory safety tests (serum biochemistry, haematology, coagulation, thyroid stimulating hormone [TSH], FT4 and urinalysis).

Blood samples for biomarker (tryptase) will be collected immediately after any possible allergic or anaphylactic adverse reaction, and 12 hours later. These samples will only be analysed if relevant adverse reactions occur.

The PK evaluation will include measurement of plasma Y14 levels and associated PK parameters.

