5.1.5 Discussion of Study Design

This is a double-blinded, randomised, placebo-controlled study in two parts: a single ascending dose study and multiple ascending doses, to investigate the effects of Y14. Note, with the exception of Cohort 1 TP1 which is partially blinded as this will be a crossover design where the volunteers will return for 3 treatment periods. The time interval between each TP should be no less than 1 week. As Y14 is intended as an anti-obesity drug, overweight/obese subjects have been chosen to provide more clinically relevant PK and PD information. With regards to Part B, we propose to recruit patients with Type 2 diabetes or pre-diabetes in order to study the impact of Y14 on glycaemia.

It is the intent of Part B to dose volunteers such that steady-state is achieved and maintained for several days. Based on the available pre-clinical data it is expected that this will be achieved following 28 days once weekly dosing, however, a full review of all the safety, tolerability and pharmacokinetic data from Part A will be performed to confirm the dose regimen for Part B. If

CONFIDENTIAL

the elimination half-life of Y14 is shorter than anticipated from the pre-clinical data, more frequent dosing (e.g. twice weekly) may be appropriate. If the elimination half-life of Y14 is longer than anticipated from the pre-clinical data, dosing every two weeks may be more appropriate (as steady-state will take longer to achieve). The dose frequency will be no more frequent than once a day and no less frequent than once every 14 days. The dosing duration will not exceed 29 consecutive days of dosing.

Details of the dosing regimen and duration used for Part B of the study will be documented in the SMF.

The sample size (approximately 28 subjects in Part A [SAD] and 24 subjects in Part B [MAD]) has been chosen to minimise the number of subjects exposed to Y14 whilst obtaining sufficient information to assess the safety, tolerability, PK and PD of Y14.

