7.2.2 Energy Intake

Energy intake will be recorded for Part A and Part B.

A formal 24 h food intake study will be carried out on Part A from Cohort 3 onwards, on Day -1 (measuring lunch and dinner on Day -1 and breakfast on Day 1) and Day 1 (measuring lunch and dinner on Day 1 and breakfast on Day 2).

For Part B, the food intake studies will be carried out on Days -1, 2, and 30. The food intake study on Day -1 will measure the ad libitum intake of food during breakfast, lunch and dinner on Day -1. The food intake study on Day 2 will measure the ad libitum intake of food during breakfast, lunch and dinner on Day 2. The food intake study on Day 30 will measure the ad libitum intake of food during breakfast, lunch and dinner on Day 30. The timing of the food intake study will be altered according to emerging PK data, if the t_{max} is delayed beyond 24 hours. If the timing of the food intake studies are changed the times of the OGTT samples may also be changed to ensure they do not happen on the same day.

While resident in the clinical unit during 24 h food intake assessment days, subjects will be individually provided meals in a designated area with individual cubicles per subject. Meals will be presented with an excess of food and subjects will be asked to eat until they feel "comfortably full" within a period of 30 minutes. Should a volunteer require more time to eat, an extra 15 minutes will be allowed, but such an event will be recorded as a deviation from protocol. The energy value of each component of the meal will be determined. Food will be weighed pre- and post-meal to determine consumption.

CONFIDENTIAL

Synoptic Clinical Study Protocol
Version 2.0 - 05/08/2017

EudraCT Number: 2017-000380-33

For other days in Part A and Part B, energy intake will be carried out semiquantitatively i.e. clinical research unit staff will record the timing, types and amounts of food eaten by subjects. For the semiquantitative measurement, at the end of each meal the percentage of food left will be assessed to be either <10%, 10-<25%, 25-<50% or ≥50%. Snack boxes will also be provided at certain timepoints whilst resident in the clinical unit (to be specified in the Meal Manual).

In Part B, subjects will be admitted on Day -2 (2 days prior to dosing) in order to acclimatise to the clinical research unit and obtain baseline food consumption measurements.

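### Minor, Part A only: review PK to 72 h before escalating between cohorts, and require later review when concentrations are still rising

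*Combined protocol and SAP*

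**What the plan says.** Section 5.1.4 (Stopping Rules) halts escalation in Parts A and B if "The mean systemic exposure is predicted to exceed a C_{max} of 440 ng/mL and/or $AUC(0-72h)$ of 28,100" ng·h/mL. The limits are tied to the lowest exposure at the NOAEL in male rats.

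Section 5.1.1 sets the data behind each Part A decision: "Safety, tolerability and PK data will be reviewed up to 48 hours post-dose prior to the dose escalation decision". It then adds an exception: "If T_{max} is significantly later than predicted, PK data to a later timepoint may be reviewed prior to the dose escalation decision". The predicted Tmax is not given, and the size of delay that counts as significant is not defined.

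The same section keeps each Part A subject in the unit until 72 h after the dose "or until C_{max} is achieved, whichever is the later". On timing between cohorts it says: "An interval of at least 7 days will separate the dosing of the last subject in one cohort" and the first dose in the next. Inside Cohort 1 a different spacing applies: "There will be a minimum washout period of 1 week between Day 1 of each TP".

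Section 7.2.2 moves the food intake study "if the t_{max} is delayed beyond 24 hours". Section 3.2 describes Y14 as a sustained-release formulation.

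**The concern.** The AUC limit covers 72 h, and the Cmax limit applies whenever the peak occurs, but the default review stops at 48 h. The stay rule waits for a late peak. The review rule does not have to, even after a late Tmax is recognised, because its exception is permissive.

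If concentrations are still rising at 48 h, the reviewers have not seen the peak. What they conclude about Cmax then depends on how they project it, and the documents give no method. This is the only numeric exposure limit among the escalation stopping rules of a first-in-human study, so it is better applied to observed data where such data can be had at little cost.

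**Working it through.** **Inputs from the documents.** Cmax limit 440 ng/mL and AUC(0-72h) limit 28,100 ng·h/mL (5.1.4). Default review to 48 h, stay to at least 72 h, at least 7 days between cohorts (5.1.1). The limits rest on rat data outside the documents and cannot be re-derived.

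**Exact bounds on the AUC limit.**
- If Cmax is at most 440, AUC(0-48h) is at most 48 × 440 = 21,120, and 21,120 / 28,100 = 75% of the limit. On 48 h data the AUC limit can act alone only through extrapolation.
- The AUC limit binds before the Cmax limit only if the 0-72 h average exceeds 28,100 / 72 = 390 ng/mL with a peak of at most 440, an average-to-peak ratio above 390 / 440 = 0.887.
- The largest AUC excess with Cmax within its limit is 440 × 72 / 28,100 = 31,680 / 28,100 = 1.127, or 13%.

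**Assumed profiles.** The documents give no human PK for Y14. The grid is a one-compartment model with first-order absorption: absorption half-life a of 2, 6, 12, 24, 36 or 48 h, crossed with elimination half-life e of 24, 48, 72, 120, 168 or 240 h, giving 36 single-dose profiles. Up to a constant, C(t) = 2^(−t/e) − 2^(−t/a), or t × 2^(−t/a) when a = e. Only ratios are used, so dose and volume cancel.

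**AUC limit on the grid.** Cmax binds first in 35 of 36 profiles. The exception (a = 2, e = 240) exceeds the AUC limit by 2%. Data to 48 h hold 50% to 84% of AUC(0-72h), but log-linear extrapolation from 24-48 h errs only 0 to +7%, on the safe side.

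**Peak on the grid.** In 12 of 36 profiles the highest value by 48 h is below 95% of the highest by 72 h. All 12 have Tmax of about 69 h or later and an absorption half-life of at least 24 h. With an absorption half-life of 12 h or less, the shortfall is below 0.5%.

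Two profiles can be checked by hand:
- *Lowest raw reading, a = 48, e = 240 (Tmax 139 h).* C(24) = 0.9330 − 0.7071 = 0.2259; C(48) = 0.8706 − 0.5000 = 0.3706; C(72) = 0.8123 − 0.3536 = 0.4587. Raw maximum at 48 h: 0.3706 / 0.4587 = 0.81, or 19% low. Log-linear value at 72 h: 0.3706 × (0.3706 / 0.2259) = 0.608, and 0.608 / 0.4587 = 1.325, or 32% to 33% high.
- *Highest extrapolated reading, a = e = 48 (Tmax 69 h).* C(24) = 16.97, C(48) = 24.00, peak 25.48. Raw: 24.00 / 25.48 = 0.94. Log-linear: 24.00 × (24.00 / 16.97) = 33.94, and 33.94 / 25.48 = 1.33.

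Across the 12 profiles the log-linear reading is 29% to 33% high. The 0-72 h peak judged from 48 h data therefore runs from 19% low to 33% high, depending on the method.

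**What 72 h data add.** They replace that range with an observed 0-72 h peak and an observed AUC(0-72h). They do not settle profiles that peak after 72 h. In the first example the 48 h maximum is 69% of the eventual Cmax, so the 72 h value is 0.69 / 0.81, about 86% of it. A separate trigger for rising levels is therefore needed.

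**Calendar.** From the last reviewed sample to the earliest next-cohort dose there are 7 − 2 = 5 days now, and 7 − 3 = 4 days with 72 h data.

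**The case against.** The strongest reply is that the rule concerns predicted exposure, so extrapolation is intended. In all 12 late-peak profiles the 48 h concentration is 37% to 64% above the 24 h value, so a 48 h package already shows the rise. Taking the larger of the observed maximum and the log-linear 72 h value never under-predicts the 0-72 h peak in any of the 36 profiles. The late-Tmax clause is aimed at these cases: section 7.2.2 suggests a Tmax expected within about 24 h, so 69 h would be late. The prediction method may be in the separate Pharmacokinetic Analysis Plan named in section 9.1, which is not in the documents. The grid is assumed, and its troublesome corner needs slow absorption that no document supports.

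Most of this stands, and it is why the point is minor. What survives is narrow. No method is stated, the safe one can overstate the peak by a third, and the clause for late peaks does not oblige anyone to use it.

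A reader might infer more, and three such readings fail:
- *That 5.1.4 and 5.1.1 contradict each other, or that the AUC limit cannot be enforced.* A predictive rule can work from 48 h data, and the AUC extrapolation error on the grid is small and on the safe side.
- *That the next dose could really reach 440 / 0.81, about 545 ng/mL.* This requires reviewers to treat a visibly rising 48 h value as Cmax and scale it. The protocol does not prescribe that, and the documents do not show how near the planned doses come to the limits.
- *That Part B has the same gap.* Section 5.1.5 says "It is the intent of Part B to dose volunteers such that steady-state is achieved and maintained for several days", and profiles near steady state are flatter. On the same grid after the fifth weekly dose, 48 h data hold at least 98.5% of the 0-72 h peak and the log-linear AUC error is 0 to +4%. Section 5.1.2 already draws on data from previous doses and keeps Part B doses within what Part A showed to be tolerable.

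**Conclusion.** The point holds as a minor, inexpensive improvement to Part A. The mismatch between a 48 h default review and limits on Cmax and AUC(0-72h) is plain in the text, and so is the optional wording on late PK. Its consequence is confined to late-peaking profiles, where the 0-72 h peak is uncertain by about −19% to +33% until later samples are read. That range, and the Tmax threshold of about 69 h, rest on the assumed one-compartment grid; another model would move them. The exact bounds (75%, 0.887 and 13%) need no PK model. Nothing here shows that the stopping rule fails, and the clinical stopping rules operate independently of it.

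**What to change.** Make two changes in section 5.1.1, for Part A only:
1. Review PK to 72 h after the dose before escalating from one cohort to the next, and derive AUC(0-72h) from those data.
2. In the sentence on late Tmax, replace 'may' with 'will', and tie it to an observable trigger: PK beyond the last reviewed sample must be reviewed when the mean concentration is still rising at that sample.

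For the steps inside Cohort 1, keep the 48 h review if assay turnaround requires it. There the spacing is one week between Day 1s, and in the first period the sentinel pair is dosed at least 48 h before the others. If that pair starts the second period first, only 7 − 2 = 5 days follow the last first-period dose. That leaves 5 − 2 = 3 days after a 48 h sample and 5 − 3 = 2 days after a 72 h sample.

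The cost is two sentences of wording, one partial AUC per decision, and one day less for assay and quality control between cohorts. Assay turnaround and the 72 h sampling time are not in the documents, so the sponsor should confirm both. The decision is delayed further only when levels are still rising, and the gap may then need to exceed 7 days. No dose, limit or cohort size changes, and Part B stays as written.

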5.1.5 Discussion of Study Design

This is a double-blinded, randomised, placebo-controlled study in two parts: a single ascending dose study and multiple ascending doses, to investigate the effects of Y14. Note, with the exception of Cohort 1 TP1 which is partially blinded as this will be a crossover design where the volunteers will return for 3 treatment periods. The time interval between each TP should be no less than 1 week. As Y14 is intended as an anti-obesity drug, overweight/obese subjects have been chosen to provide more clinically relevant PK and PD information. With regards to Part B, we propose to recruit patients with Type 2 diabetes or pre-diabetes in order to study the impact of Y14 on glycaemia.

It is the intent of Part B to dose volunteers such that steady-state is achieved and maintained for several days. Based on the available pre-clinical data it is expected that this will be achieved following 28 days once weekly dosing, however, a full review of all the safety, tolerability and pharmacokinetic data from Part A will be performed to confirm the dose regimen for Part B. If

CONFIDENTIAL

the elimination half-life of Y14 is shorter than anticipated from the pre-clinical data, more frequent dosing (e.g. twice weekly) may be appropriate. If the elimination half-life of Y14 is longer than anticipated from the pre-clinical data, dosing every two weeks may be more appropriate (as steady-state will take longer to achieve). The dose frequency will be no more frequent than once a day and no less frequent than once every 14 days. The dosing duration will not exceed 29 consecutive days of dosing.

Details of the dosing regimen and duration used for Part B of the study will be documented in the SMF.

The sample size (approximately 28 subjects in Part A [SAD] and 24 subjects in Part B [MAD]) has been chosen to minimise the number of subjects exposed to Y14 whilst obtaining sufficient information to assess the safety, tolerability, PK and PD of Y14.

5.2 Study Population

Approximately 28 subjects will be enrolled in Part A (SAD) and 24 subjects will be enrolled in Part B (MAD).

Overweight male volunteers will be entered into this study provided that they satisfy the following inclusion/exclusion criteria.

5.2.1 Subject Inclusion Criteria

1. Adult males aged 18 to 65 years inclusive with BMI between 25.0 and 38.0 kg/m² inclusive;
2. (PART B only) Subjects who have normal glucose tolerance, Type 2 diabetes, impaired glucose tolerance or impaired fasting glucose according to WHO 2006 and 2011 criteria,
 - a) In subjects who are identified as being prediabetic or diabetic, they should be stably treated either with:
 - i. diet only;
 - ii. monotherapy with a sulphonylurea, metformin, or a SGLT-2 inhibitor;
 - iii. dual therapy with a sulphonylurea, metformin, and/or a SGLT-2 inhibitor;
 - iv. or triple therapy with a sulphonylurea, metformin, and a SGLT-2 inhibitor.

Patients treated with other anti-diabetic treatments are excluded.

- b) In subjects who are identified as being prediabetic or diabetic, the HbA1c at screening should be 6 - 8.5% (42 - 69 mmol/mol) and <±1.0% (±11 mmol/mol) from a previous HbA1c reading within the last 6 months, where available. Where an HbA1c reading within the last 6 months is not available, the subject should have HbA1c re-measured after at least 4 weeks to assure stability of glycaemia before inclusion in the study. This remeasurement may take place any time up to and including check in on Day -2.
- c) To allow assessment of eligibility, subjects without known diabetes or prediabetes, or in whom the glycaemic status is in doubt, may undergo a pre-screening visit no more

CONFIDENTIAL

than 10 weeks before Day 1 for assessment of fasting glucose, HbA1c and glucose 2 hours after a 75 g oral glucose tolerance test.

3. Subjects who are otherwise healthy enough to participate, as determined by pre-study medical history, physical examination and 12-lead ECG;
4. Subjects whose clinical laboratory test results are either within the normal range or if outside this range the abnormalities are judged to be not clinically relevant and are acceptable to the Investigator;
5. Subjects who are negative for hepatitis B surface antigen (HBsAg), hepatitis C antibody and human immunodeficiency virus (HIV) I and II tests at screening;
6. Subjects who are negative for drugs of abuse and alcohol tests at screening and admissions;
7. Subjects who are non-smokers for at least 3 months preceding screening;
8. Subjects who agree to use medically acceptable methods of contraception for at least 3 months after study drug administration;
9. Subjects who agree not to donate sperm for at least 3 months after study drug administration;
10. Subjects who are able and willing to give written informed consent.

Subjects' medical history must be verified by either a personal physician or medical practitioner as appropriate.

